#### **Assessment of gastroparesic symptoms, quality of life and use of TEA**

Dyspeptic and gastroparesic symptom questionnaire will use the previously validated gastroparesis cardinal symptom index (17), including 9 symptoms: nausea (feeling sick to your stomach as if you were going to vomit or throw up), retching (heaving as if to vomit, but nothing comes up), vomiting, stomach fullness, not able to finish a normal sized meal, feeling excessively full after meals, loss of appetite, bloating (feeling like you need to loose your clothes) and stomach or belly visibly larger. Each symptom will be graded from 0 to 5 (none, very mild, mild, moderate, severe and very severe).

Quality of life questionnaire Health-related QOL (HR-QOL, or QOL) symptom assessment will be performed using the validated SF-36 health form questionnaire with its specific scoring system.

Fig.2: The micro-stimulator (watch-like) to be used for TEA.

TEA use questionnaire 1) How many meals did you eat in the last 7 days? 2) How many of these meals did you apply the TEA? 3) When you use the TEA, about how long do you wear the stimulators?

### **Assessment of symptoms for patients with chronic constipation**

Symptoms: 1) Number of spontaneous complete bowel movement (SCBM) per week. 2) Patient Assessment of Constipation Symptoms (PAC-SYM). Stool diary during the entire experimental period to assess bowel movement, including number and time of defecation, stool quality, straining and medications or any other methods used for defecation; stool consistency will be assessed according to the Bristol Stool Form Scale. PAC-SYM questionnaire will be completed every two weeks. 3) Quality of life (PAC-QoL): the questionnaires will be completed at all visits.

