Upon enrollment, each patient will be randomly assigned to group A or group B. Patients in group A will be treated with TEA at ST36 and PC6 for 4 weeks, followed with a 2-week washout period and another 4-week period with sham TEA. Patients in group B will be treated with TEA and sham-TEA in a reversed order. The previous preliminary studies with EA or TEA were of duration of 2 weeks. To ensure better performance, we choose a treatment period of 4 weeks. A previous study has indicated that a washout period of 2 weeks is sufficient. The patients will not be informed of the exact locations of ST36 or PC6 and will not be informed that TEA at the sham points may be ineffective. The patients will be asked to come to the hospital 4 times: before the study (V1), end of the first 4 weeks (V2), end of washout period or beginning of the second 4-weeks (V3) and end of the second 4 weeks (V4). TEA or sham TEA will be performed three times daily, each initiated immediately after a meal and lasts for 2 hours. Various tests will be performed during each visit (see Fig.1 and Table 1). Symptoms of gastroparesis, assessment of constipation and questionnaire of quality of life (SF-36) as well as

TEA usage questionnaire will be completed during each of the 4 visits. The questionnaires will also be completed by the patient at home at the end of each week including the washout period.

The procedure for each visit is as follows: In the morning, GI symptom questionnaire, TEA use and SF-36 will be completed; then chest and abdominal surface electrodes will be placed and the noninvasive measurements of electrogastrogram (EGG) will be recorded for 2 hours. One hour after the recording, a test meal will be consumed by the subject and the recording will be continued for one more hour. Blood samples will be taken to measure gastrointestinal hormones such as NPY, ghrelin, CCK, motilin and VIP at different time points: at the initiation of the baseline recording of the EGG, immediately before the ingestion of the meal, 30 and 60min after the test meal. TEA or sham-TEA (according to the preceding treatment regime) will be performed during the tests for visits 2 and 4. No TEA or sham-TEA will be performed during visits 1 and 3 as these tests will be considered as baseline or control tests. For the patients with chronic constipation, no nutrient drink test will be conducted, symptoms related to constipation will be assessed, EGG will be recorded and blood samples will be collected.

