### **b. Study duration and number of study visits required of research participants.**

The study duration will be for 10 weeks, each patient will have 4 visits.

c. Blinding, including justification for blinding or not blinding the trial, if applicable.

Blinding of investigator is not practical as the investigator will be performing the procedure such as locate acupoints or sham-acupoints. However, the patients will be blinded to the TEA/sham TEA treatment.

d. Justification of why participants will not receive routine care or will have current therapy stopped.

Not Applicable.

e. Justification for inclusion of a placebo or non-treatment group.

Not Applicable. All the patients will have TEA treatment.

f. Definition of treatment failure or participant removal criteria.

Treatment failure will be defined as a lack of improvement in symptoms pre and post TEA treatment based on validated questionnaires and gastric motility assessment 6 and 12 months after the last treatment. Participant removal criteria will include any patient with moderate to severe adverse reaction to TEA or inability to tolerate the TEA conforming to standards of usual routine care.

g. Description of what happens to participants receiving therapy when study ends or if a participant's participation in the study ends prematurely.

The participant will follow up with their referring gastroenterologist and continued therapy will be left to the discretion of their provider.

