#### Inclusion criteria for chronic constipation patients

1. Satisfying Rome IV criteria for diagnosis of functional constipation;
2. abdominal X-ray or anorectal manometry test during the past 3 months indicating delayed colonic transit (more than 20% ingested markers are retained) or abnormal colonic motility;
3. ages 18-80 years;
4. no constipation medication for a minimum of 1 week before enrollment except for rescue agents (stimulant laxatives, such as bisacodyl);
5. willing to comply with the treatment regimen.

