## 7. Study Statistics

### a. Primary outcome variable.

The primary outcome of this study is GI symptoms including weekly GI symptom questionnaire; number of spontaneous complete bowel movement (SCBM) per week; and Patient Assessment of Constipation Symptoms (PAC-SYM), once every two weeks.

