### c. Statistical plan including sample size justification and interim data analysis.

Analysis of the outcomes will use a repeated measures regression model including fixed effects for treatment, patient and time period. The model will be estimated using 8 weekly observations (weeks 1-4 and 7-10) on percentage changes in symptoms score from baseline visit (V0) levels for each subject. Results will be expressed as least squares means for the percentage change in symptoms score observe under each treatment, and statistical significance of any difference between these means will be determined with a model-based t-test. A weekly estimate of percentage compliance with the prescribed TEA-use regimen based on patient response to the TEA-use questionnaire will be included in the estimated model as a covariate to address possible confounding of treatment and compliance effects.

In the current protocol, 40 FD patients, 40 gastroparesis patients and 40 constipation patients will be enrolled. The accuracy of the planned patients sample in each disease was assessed by Monte Carlo stimulation. Each simulated sample assumed the percentage change in symptom score outcome is normally distributed with a standard deviation of 38 and a correlation of 0.4 across repeated observations on the same subject. This parameterization was based on previous data from a similar cross-over study by Liu et al. comparing the effects active and sham TEA administered with a conventional TENS device on changes in the same gastrointestinal symptom score in functional dyspeptic patients (14). Results of the power simulation indicate that with complete follow-up the planned sample provides an 80% chance of detecting a cross-treatment difference in symptom score change equal to 10-11 percentage points with a two-sided significance level of 0.05. Even if 40% of follow-up data are missing at random due to drop-outs or missed follow-up contacts, the simulation results indicate the planned experiment would still have an 80% chance of detecting a cross-treatment difference in symptom score change of 13-14 percentage points with a two-sided significance level of 0.05.

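### No diary week before treatment is scheduled for weekly SCBM, so the baseline that the percentage-change analysis divides by has no defined source

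*Combined protocol and SAP*

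**What the plan says.** Section 7a lists "number of spontaneous complete bowel movement (SCBM) per week" among the primary outcomes. The section on symptom assessment in chronic constipation gives the only described source of bowel-movement counts: "Stool diary during the entire experimental period to assess bowel movement, including number and time of defecation, stool quality, straining".

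On timing, section 4a says group A "will be treated with TEA at ST36 and PC6 for 4 weeks, followed with a 2-week washout period and another 4-week period" on sham, with group B in reverse order. It places the first two visits "before the study (V1), end of the first 4 weeks (V2"). Section 4b adds: "The study duration will be for 10 weeks, each patient will have 4 visits". No stimulation is given during V1, whose tests serve as baseline. Section 4a also has a constipation assessment completed at each of the four visits, but does not describe its content.

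Section 7c gives one model, introduced as the analysis of the outcomes in general. It has treatment, patient and time-period effects, and its response is "percentage changes in symptoms score from baseline visit (V0) levels for each subject", observed in weeks 1-4 and 7-10. No visit called V0 is defined; V1 is the only visit before treatment.

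Table 1 is headed for FD and gastroparesis patients only. Section 5 requires of constipation patients "no constipation medication for a minimum of 1 week before enrollment except for rescue agents", without attaching a diary to that week.

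**The concern.** A weekly SCBM count is a total over seven days and cannot be observed on the day of a visit. The analysis needs one such total per patient from before treatment, and the schedule provides no week in which to record it. The team would then have to fill the gap, most likely with a number recalled at V1. That would set a recalled count against prospectively recorded diary counts inside the same change score.

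At stake is the analysis of one of the two constipation-specific primary outcomes. A diary week before treatment cannot be recovered once stimulation has begun, so this is easy to repair now and impossible later. PAC-SYM is not affected in this way, because a questionnaire can be completed at V1.

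**Working it through.** **1. Timeline.** The inputs are the period lengths in section 4a and the duration in section 4b.

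- Treatment 4 + washout 2 + treatment 4 = 10 weeks, which reproduces the stated duration.
- Weeks left for a run-in: 10 - 10 = 0.
- Diary days: 10 x 7 = 70, of which 0 precede treatment. V1 is week 0 and V2 closes the fourth treatment week, so treatment weeks 1-4 follow V1 directly.

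**2. Candidate sources for the baseline.**

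- *Constipation assessment at V1:* takes place before treatment, but no SCBM item or recall window is stated.
- *Medication-free week in section 5:* an eligibility condition with no diary.
- *Washout diary (weeks 5-6):* recorded, but after period 1 treatment, and section 7c refers to a baseline visit.
- *Week 1:* one of the eight outcome weeks in section 7c, so not a baseline under the plan.

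Only the first is possible as written, and it is undefined.

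**3. Where a faulty baseline does harm.** For patient i, let T and S be the mean weekly diary counts on TEA and on sham, b the true baseline and k x b the baseline actually recorded.

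- Absolute change: (T - kb) - (S - kb) = T - S. The baseline cancels whatever k is. In a model with patient effects it is a patient constant and is absorbed.
- Percentage change: 100(T - kb)/(kb) - 100(S - kb)/(kb) = 100(T - S)/(kb). The true contrast is divided by k.
- If k is the same for everyone, the estimate and its standard error are both divided by k. The reported effect is rescaled but the t statistic does not change.
- If k differs between patients, each contrast is divided by a different amount, and the error passes into both the estimate and its precision.

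The documents give neither an SCBM rate nor any information on recall error, so the size of this cannot be calculated. The SD of 38 and correlation of 0.4 in section 7c come from a symptom score in functional dyspepsia and do not help.

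**4. Would a diary baseline alone rescue the percentage scale?** Assume, for illustration, that weekly counts are Poisson with mean m. The chance that a 7-day baseline is zero, leaving percentage change undefined, is exp(-m).

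| Assumed mean SCBM per week | P(zero baseline) | Expected number of 40 patients |
|---|---|---|
| 0.5 | 0.607 | 24.3 |
| 1 | 0.368 | 14.7 |
| 2 | 0.135 | 5.4 |
| 3 | 0.050 | 2.0 |

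So a run-in diary is necessary for a sound description of change, but does not make the stated analysis workable.

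**The case against.** The strongest reply is that a crossover with patient effects does not need a baseline. The diary covers all eight treatment weeks, so the randomised within-patient comparison of TEA with sham is fully collected. This stands, and it limits the severity. A reader might infer that the missing diary week spoils the comparison on any scale; step 3 shows that the contrast is harmed only through the percentage divisor. On absolute change, only the description of improvement from baseline suffers.

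A second reply is that V1 includes a constipation assessment, which might contain a 7-day recall question; the TEA-use questionnaire already asks about the past 7 days. This also stands in part. A reader might infer that no baseline is collected at all, but the documents show only that its source is undefined and that it is not the diary.

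A third stronger reading is that week 1 would serve as baseline, building treatment effect into it and making it depend on sequence. The documents do not propose this.

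Two further points temper confidence. Section 7c speaks of a symptom score, and SCBM is a count. Applying the model to SCBM rests on its being stated for the outcomes generally; if it does not apply, this primary outcome has no analysis at all, and the text still needs changing. Also, Figure 1 could not be seen in the text available, and the term experimental period is not defined. A run-in shown there would answer the scheduling point, though it would not fit within the stated 10 weeks.

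**Conclusion.** The point holds in this form: no pre-treatment diary week is scheduled for SCBM, the only possible V1 source is unspecified and would not match the diary, and the only stated analysis divides by that baseline. The documentary size is 0 of 70 diary days before treatment, in one cohort of 40 patients. The effect on the TEA-sham estimate cannot be quantified from the documents.

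The conclusion rests on two readings: that the diary starts with the 10-week study, and that the section 7c model covers SCBM. The zero-baseline figure of about 37% further assumes Poisson counts with a mean of 1 per week.

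This should be fixed before enrolment in the constipation cohort. It does not invalidate the trial, because weekly diary counts under both treatments are still obtained from the same patients.

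**What to change.** **Collection.** In the constipation cohort, issue the stool diary at consent or teleconsent, at least 7 days before V1. Define baseline SCBM as the count over the 7 diary days immediately before first stimulation. Add a constipation version of Table 1 with a Week -1 diary row, and replace V0 in section 7c with a defined time point.

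**Analysis.** In section 7c, analyse weekly on-treatment SCBM counts (weeks 1-4 and 7-10) directly within patient, with treatment, patient and period effects, for example in a count model. Use the diary baseline only to describe absolute change, so that nothing is divided by a count that may be zero.

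**Cost.** A short amendment, one extra diary week per constipation patient, and treatment starting up to a week later. No extra visit is needed, since section 4a already allows teleconsent and the diary is an existing instrument. Whether the diary week can coincide with the medication-free week in section 5 depends on when enrolment is counted, which the amendment should state.

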### **Measurements of EGG and GI hormones**

The noninvasive measurement of the EGG will be made and blood samples will be taken in order to answer the following questions: 1) whether there is an alteration or impairment in gastric slow waves, vagal activity and/or certain gastrointestinal hormones in patients with FD or gastroparesis, compared with healthy controls; 2) whether TEA is able to improve the impairment if any; 3) if TEA improves some of these abnormalities, whether the improvement is correlated with the improvement in FD or gastroparesis.

*The EGG measurements* will be made in each patient during each visit (starting at 9am) with the following protocol: a 30-min baseline recording without TEA or sham-TEA, another 30-min recording with TEA or sham-TEA, consumption of the test meal for the gastric emptying test described above and a 60-min postprandial recording. Blood samples (5ml) will be drawn at the beginning of the tests, beginning of the meal and 30-min and 60-min after the meal.

*Recording and analysis of the EGG:* A noninvasive method, called electrogastrography, will be used in this study to assess the effects of acute and chronic TEA on gastric slow waves (18). The EGG will be recorded using a multichannel recording device which is a standard piece of FDA-approved clinical equipment. The device consists of four identical amplifiers with cut-off frequencies of 1.8 and 16.0 cpm (19). The data will be converted from analogue to digital with a sampling frequency of 1Hz on line and stored. Patients will remain at 30 degrees head elevation and be required to remain motionless in order to avoid possible artifacts derived from body movements. Four-channel EGG signals will be recorded. Previously validated spectral analysis methods will be used to derive the following parameters from the EGG (19): a) dominant frequency and power of the slow waves; b) the percentage of normal 2-4 cycles/min slow waves and c) the percentage of tachygastria, bradygastria or arrhythmia.

*Measurement and analysis of GI hormones:* A number of GI hormones/neuropeptides are involved in the regulation of gastric motility. The major excitatory neuropeptides include motilin, ghrelin, neuropeptide Y (NPY), cholecystokinin CCK and substance P, whereas vasoactive intestinal peptide (VIP) and nitric oxide are the major inhibitory neuropeptides. Electroacupuncture has been shown to be effective in altering ghrelin, NPY and VIP in rats (22-24). Little information is available on the effects of EA in patients with motility disorders. In our preliminary studies, we observed an increase in NPY with TEA in patients with functional dyspepsia and a decrease in VIP with TEA in patients with scleroderma. In this study, we choose to study the effects of TEA on NPY, ghrelin, CCK, motilin and VIP.

Blood samples will be collected in chilled EDTA tubes, centrifuged at 2°C for 10 minutes, and stored at -70°C until extraction. Plasma NPY, VIP, motilin, CCK and ghrelin levels will be determined using commercially available radioimmunoassay kits. In addition, some blood samples will be reserved for the analysis of other hormones related to GI motility and sensation.

### **b. Study duration and number of study visits required of research participants.**

The study duration will be for 10 weeks, each patient will have 4 visits.

c. Blinding, including justification for blinding or not blinding the trial, if applicable.

Blinding of investigator is not practical as the investigator will be performing the procedure such as locate acupoints or sham-acupoints. However, the patients will be blinded to the TEA/sham TEA treatment.

d. Justification of why participants will not receive routine care or will have current therapy stopped.

Not Applicable.

e. Justification for inclusion of a placebo or non-treatment group.

Not Applicable. All the patients will have TEA treatment.

f. Definition of treatment failure or participant removal criteria.

Treatment failure will be defined as a lack of improvement in symptoms pre and post TEA treatment based on validated questionnaires and gastric motility assessment 6 and 12 months after the last treatment. Participant removal criteria will include any patient with moderate to severe adverse reaction to TEA or inability to tolerate the TEA conforming to standards of usual routine care.

g. Description of what happens to participants receiving therapy when study ends or if a participant's participation in the study ends prematurely.

The participant will follow up with their referring gastroenterologist and continued therapy will be left to the discretion of their provider.

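### Patients removed for intolerance to TEA lose some or all of their weight in the TEA versus sham contrast, so the estimate leans towards patients who tolerate the device

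*Combined protocol and SAP*

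**What the plan says.** Section 4f (treatment failure and removal) gives the rule: "Participant removal criteria will include any patient with moderate to severe adverse reaction to TEA or inability to tolerate the TEA". Section 4g covers participation that ends early: "The participant will follow up with their referring gastroenterologist and continued therapy will be left to the discretion of their provider". Neither section, nor any other, says that symptom questionnaires continue after removal. The documents define no analysis population and no intention-to-treat rule.

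Section 4a sets out the crossover: "Patients in group A will be treated with TEA at ST36 and PC6 for 4 weeks, followed with a 2-week washout period", then four weeks of sham. Group B has the reverse order. Questionnaires are completed at home every week, washout included.

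Section 7c analyses percentage change in symptom score at weeks 1-4 and 7-10 with "a repeated measures regression model including fixed effects for treatment, patient and time period". Weekly compliance "will be included in the estimated model as a covariate to address possible confounding of treatment and compliance effects". Missing data appear only in the sample size paragraph, as a scenario in which 40% of follow-up is "missing at random due to drop-outs or missed follow-up contacts".

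The removal rule names TEA only. The description of TEA and sham-TEA in section 4a gives sham the same stimulator output at different points, so intolerance can arise on either.

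**The concern.** In a model with fixed patient effects, the treatment effect is estimated only from differences within a patient. A patient who leaves during the first period has no such difference. However badly that patient fared, the result cannot change the treatment contrast directly.

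Because the reason for leaving is the reaction to stimulation, those who drop out of the contrast are selected on tolerability. The objective in section 2 concerns patients with functional dyspepsia, gastroparesis or constipation, not the subset who can wear the device for two hours after each of three daily meals. If intolerant patients benefit less, the reported effect is larger than the effect in everyone randomised.

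**Working it through.** **The plan's own figure.** Inputs from section 7c: SD 38, correlation 0.4, 40 patients per disease, four weekly observations per period, two-sided 0.05, 80% power. For a within-patient contrast with constant correlation:

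SE = sqrt(2 x 38² x (1 - 0.4) / (4 x 40)) = sqrt(10.83) = 3.29; detectable difference = (1.960 + 0.842) x 3.29 = 9.2 points.

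The plan states 10-11, so its figure is not reproduced and is slightly conservative. For 40% missing it states 13-14 points. Simulation at n = 40 roughly agrees: 82% power at 13 points with scattered missingness, and about 80% at 13.5-14 with monotone dropout. The point below does not depend on either figure.

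**Weight of each patient.** With n1 and n2 weekly observations in the two periods, a patient's weight in the contrast is n1 x n2 / (n1 + n2).

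- Completer: 4 x 4 / 8 = 2.
- Removed in period 1 after two weeks: 2 x 0 / 2 = 0.
- Removed in period 2 after two weeks: 4 x 2 / 6 = 1.33.

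**Check of the zero weight.** In a simulated data set of 40, four group A patients were removed after week 2. The estimate was the same whether their data were kept, raised by 500 points or deleted: -5.447 with a period effect and, in a second data set, -12.236 with week effects. With the compliance covariate added, the 500-point shift again changed nothing. Deletion moved the estimate only through the compliance slope (-13.755 to -13.757; -13.868 to -13.913).

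**Illustrative size.** Assumptions, none from the documents: a fraction q is intolerant; the effect is 0 in them and -10.5 in the others (the middle of the plan's 10-11); removal follows two weeks of the triggering device; allocation is 1:1. The all-randomised effect is -10.5 x (1 - q).

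*Only real TEA triggers removal.* Intolerant patients in group A (TEA first) have weight 0, so group A estimates -10.5. In group B they form a weighted share s = 1.33q / (1.33q + 2(1 - q)), so group B estimates -10.5 x (1 - s). With a period effect in the model, the result is the average of the two groups.

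*All removals in period 1.* No intolerant patient counts, the model estimates -10.5, and the shift is 10.5 x q.

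| q | All randomised | s | Model, TEA-only removal | Shift, TEA-only | Shift, all in period 1 |
|---|---|---|---|---|---|
| 5% | -9.98 | 0.034 | -10.32 | 0.35 | 0.53 |
| 10% | -9.45 | 0.069 | -10.14 | 0.69 | 1.05 |
| 20% | -8.40 | 0.143 | -9.75 | 1.35 | 2.10 |

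Simulation of the TEA-only case gave -10.32, -10.17 and -9.74, in agreement within simulation error.

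**Precision.** The loss is small. If all of 10% or 20% are removed in period 1, the effective n is 36 or 32 and the detectable difference rises from 9.2 to 9.7 or 10.3 points.

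**The case against.** The best defence is that each contributing patient is their own control, so fixed differences between tolerators and others do not confound the contrast. That stands: the issue is which population the estimate describes, and it matters only if the effect varies with tolerability, which no section shows. Removals may also be few. Amplitude is set by tolerability within a stated range, and the expected effects of stimulation are minor discomfort and mild skin irritation. That limits the likely size but does not close the gap in the plan.

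A reader might infer more than the documents support:

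- *That every patient who cannot tolerate TEA is left out.* On a TEA-only reading, group B patients have completed their sham weeks before they meet TEA. They keep some weight if any TEA week is recorded.
- *That removal for a treatment reaction makes the data not missing at random.* It does not follow. Missingness that depends on treatment or on observed outcomes is compatible with missing at random.
- *That section 7c rests its analysis on a missing-at-random assumption.* The phrase is used only in the power scenario.
- *That 4 removals in 40 with a 20-point gap give a 2-point bias (0.10 x 20).* This needs all four to have zero weight. With two removed in each sequence after two weeks of TEA, s = 2.67 / (2.67 + 36) = 0.069, the intolerant share of the estimate is half of that (0.034), and the shift is (0.10 - 0.034) x 20 = 1.3 points.

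**Conclusion.** The point holds as a gap in follow-up and in the definition of who is analysed. Followed as written, the plan gives one-period patients exactly zero weight in the treatment contrast and gives period-2 removals reduced weight. The first part is algebra and needs no assumption beyond the model in section 7c and the absence of data after removal.

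Whether this biases the answer for all randomised patients, and by how much, cannot be settled from the documents. Under the assumptions above the shift favours TEA by about 0.35 to 1.35 points if only real TEA triggers removal, and by up to about 2 points if all removals fall in period 1. Against a target of 10-11 points that is modest, and with few removals or equal effects it would be negligible. The change is worth making because it is cheap, not because a large bias has been shown.

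**What to change.** Leave the clinical rule for stopping TEA unchanged, and amend the text around it.

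1. In sections 4f and 4g, separate stopping the device from leaving the study. Patients who stop continue the weekly home questionnaires already scheduled, through week 10 if they agree. This means questionnaires only and implies no further stimulation.
2. In section 7c, state that these patients are analysed by assigned sequence.
3. Run the primary analysis without the compliance covariate and keep the adjusted model as a sensitivity analysis. Compliance is measured after randomisation. Weeks off the device would enter near 0% compliance, and the model would adjust away the very weeks that step 1 collects.
4. Report the number stopping by treatment and period.
5. Reconcile the removal rule, which names only TEA, with the same-output sham: the sponsor should say whether it applies to both.

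Patients who stop in period 1 and decline further questionnaires will still have zero weight; the counts in step 4 show how many. The cost is protocol wording and a few more questionnaires, with no added visits. The effect estimate may be slightly diluted, because it would then include weeks off the device.
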